Appendix C. Pregnancy and Lactation Notification Worksheets

AMGEN Pregnancy Notification Worksheet
 Fax Completed Form to the Country-respective Safety Fax Line
SELECT OR TYPE IN A BOX

1. Case Administrative Information				
Protocol/Study Number: 20140128				
Study Design:  Interventional  Observational (If Observational:  Prospective  Retrospective)				
2. Contact Information				
Investigator Name _____		Site # _____		
Phone (____) _____		Fax (____) _____		Email _____
Institution _____				
Address _____				
3. Subject Information				
Subject ID # _____ Subject Gender:  Female  Male Subject DOB: mm ____/dd ____/yyyy _____				
4. Amgen Product Exposure				
Amgen Product	Dose at time of conception	Frequency	Route	Start Date mm ____/dd ____/yyyy _____
Was the Amgen product (or study drug) discontinued?  Yes  No				
If yes, provide product (or study drug) stop date: mm ____/dd ____/yyyy _____				
Did the subject withdraw from the study?  Yes  No				
5. Pregnancy Information				
Pregnant female's LMP mm ____/dd ____/yyyy _____  Unknown				
Estimated date of delivery mm ____/dd ____/yyyy _____  Unknown  N/A				
If N/A, date of termination (actual or planned) mm ____/dd ____/yyyy _____				
Has the pregnant female already delivered?  Yes  No  Unknown  N/A				
If yes, provide date of delivery: mm ____/dd ____/yyyy _____				
Was the infant healthy?  Yes  No  Unknown  N/A				
If any Adverse Event was experienced by the infant, provide brief details _____				

Form Completed by				
Print Name: _____			Title: _____	
Signature: _____			Date: _____	

Amgen maintains a Pregnancy Surveillance Program that collects data about pregnancy of women who have been exposed to an Amgen product directly or via male sexual partner. Information from this program and from other sources of information, will contribute to knowledge that ultimately could help patients and their doctors in the future make more informed decisions about taking an Amgen medication during pregnancy.

Effective Date: March 27, 2011

Page 1 of 1

AMGEN Lactation Notification Worksheet

Fax Completed Form to the Country-respective Safety Fax Line
 SELECT OR TYPE IN A FAX#

1. Case Administrative Information

Protocol/Study Number: 20140128
 Study Design: Interventional Observational (If Observational Prospective Retrospective)

2. Contact Information

Investigator Name _____ Site # _____
 Phone (____) _____ Fax (____) _____ Email _____
 Institution _____
 Address _____

3. Subject Information

Subject ID # _____ Subject Date of Birth: mm____/dd____/yyyy____

4. Amgen Product Exposure

Amgen Product	Dose at time of breast feeding	Frequency	Route	Start Date
				mm____/dd____/yyyy____

Was the Amgen product (or study drug) discontinued? Yes No
 If yes, provide product (or study drug) stop date: mm____/dd____/yyyy____
 Did the subject withdraw from the study? Yes No

5. Breast Feeding Information

Did the mother breastfeed or provide the infant with pumped breast milk while actively taking an Amgen product? Yes No
 If No, provide stop date: mm____/dd____/yyyy____
 Infant date of birth: mm____/dd____/yyyy____
 Infant gender: Female Male
 Is the infant healthy? Yes No Unknown N/A

If any Adverse Event was experienced by the mother or the infant, provide brief details: _____

Form Completed by:

Print Name: _____ Title: _____
 Signature: _____ Date: _____

AMGEN
 Amgen maintains a Lactation Surveillance Program that collects data about women who have been exposed to an Amgen product while breastfeeding. Information from this program and from other sources of information will contribute to knowledge that ultimately could help patients and their doctors in the future make more informed decisions about taking an Amgen medication during lactation.
 Effective Date: 03 April 2012, version 2. Page 1 of 1

Amendment 1

Protocol Title: A Multicenter, Open-label Extension (OLE) Study to Assess the Long-term Safety and Efficacy of Evolocumab

Amgen Protocol Number 20140128

Amendment Date: 22 December 2014

Rationale:

This document provides the rationale and detailed list of changes for Protocol Amendment 1, dated 22 December 2014, from the original study protocol, dated 23 June 2014.

The purpose of the amendment is to:

- Update Key Sponsor Contact information
- Minor updates and clarifications

Description of Changes:

Section: Document header

Replace:

23 June 2014

With:

22 December 2014

Section: Title page

Key Sponsor Contact(s)

Replace:

PPD [REDACTED], MD
[name]
[name]

PPD [REDACTED]
[REDACTED] [REDACTED]
[REDACTED]

With:

PPD [REDACTED]
[name]
[name]

PPD [REDACTED]
[REDACTED] [REDACTED]
[REDACTED]

Section: Title page

Add:

Amendment 1 Date: 22 December 2014

Section: Investigator's Agreement

1st paragraph

Replace:

I have read the attached protocol entitled “A Multicenter, Open-label Extension (OLE) Study to Assess the Long-term Safety and Efficacy of Evolocumab”, dated 23 June 2014, and agree to abide by all provisions set forth therein.

With:

I have read the attached protocol entitled “A Multicenter, Open-label Extension (OLE) Study to Assess the Long-term Safety and Efficacy of Evolocumab”, dated **22 December** 2014, and agree to abide by all provisions set forth therein.

[Section: Protocol Synopsis, “Study Design”](#)

Replace:

Subjects who completed study 20120153 and completed IP in 20120153 will be eligible to enroll in this study.

With:

Subjects who completed study 20120153 and completed **Investigational Product (IP)** in 20120153 will be eligible to enroll in this study.

[Section: Protocol Synopsis, “Procedures”](#)

2nd paragraph

Replace:

Subjects will visit the site on Day 1 and week 4. Thereafter, subjects will visit the site quarterly for the first year and two additional times during year 2. During these visits vital signs will be obtained and adverse events (AEs), serious adverse events (SAEs), concomitant medications will be recorded, and central laboratory tests will be performed for all subjects.

[figure not shown]
With:

Subjects will visit the site on Day 1 and week 4. Thereafter, subjects will visit the site quarterly for the first year and two additional times during year 2. During these visits vital signs will be **obtained and** adverse events (AEs), serious adverse events (SAEs), concomitant medications will be recorded, and central laboratory tests will be performed for all subjects. **In addition to the protocol-specified study procedures and assessments, investigators should continue to routinely monitor subjects**

[figure not shown]
according to local disease management guidelines and perform assessments (eg, ECG, hemoglobin A1c, eGFR, and hematology), as applicable, in routine care.

Section: Study Design and Treatment Schema

Replace:

With:

Section: Study Glossary

Add:

eGFR	estimated Glomerular Filtration Rate
HbA1c	Hemoglobin A1c

Section: 4.2, Exclusion Criteria

2nd paragraph

Replace:

1. Female subject of reproductive potential not willing to inform her sexual partner of her participation in the clinical study and to use an acceptable method(s) of birth control during treatment with evolocumab and for an additional 15 weeks after the end of treatment with evolocumab. Female subjects who have had a hysterectomy, bilateral salpingectomy, bilateral oophorectomy, bilateral tubal ligatio or who are postmenopausal are not required to use contraception.
 - Postmenopausal is defined as: Age \geq 55 years with cessation of menses for 12 months or more; Age $<$ 55 by no spontaneous menses for at least 2 years; Age $<$ 55 years and no spontaneous menses within the past 1 year, but currently amenorrheic AND with postmenopausal gonadotropin levels (luteinizing hormone and follicle-stimulating hormone levels $>$ 40 IU/L) or postmenopausal estradiol levels ($<$ 5 ng/dL) or according to the definition of “postmenopausal range” for the laboratory involved.
 - Acceptable methods of birth control include: sexual abstinence, surgical contraceptive methods (vasectomy or bilateral tubal ligation), use of hormonal birth control methods (pills, shots, implants or patches), intrauterine devices (IUDs), or two (2) barrier methods (each partner must use one barrier method) with spermicide – males must use a condom with spermicide; females must choose either a Diaphragm with spermicide, OR Cervical cap with spermicide, OR Contraceptive sponge with spermicide.

- *Note: Additional medications given during treatment with evolocumab may alter the contraceptive requirements. These additional medications may require an increase in the number of contraceptive methods and/or length of time that contraception is to be utilized after the last dose of protocol-required therapies. The investigator is to discuss these contraceptive changes with the study subject.*

With:

1. Female subject of reproductive potential not willing to inform her sexual partner of her participation in the clinical study and to use an acceptable method(s) of **effective** birth control during treatment with evolocumab and for an additional 15 weeks after the end of treatment with evolocumab. Female subjects who have had a hysterectomy, bilateral salpingectomy, bilateral oophorectomy, or who are postmenopausal are not required to use contraception.
 - Postmenopausal is defined as: Age \geq 55 years with cessation of menses for 12 months or more; Age < 55 by no spontaneous menses for at least 2 years; Age < 55 years and no spontaneous menses within the past 1 year, but currently amenorrheic AND with postmenopausal gonadotropin levels (luteinizing hormone and follicle-stimulating hormone levels > 40 IU/L) or postmenopausal estradiol levels (< 5 ng/dL) or according to the definition of “postmenopausal range” for the laboratory involved.
 - Acceptable methods of **effective birth control include: sexual abstinence (when this is in line with the preferred and usual lifestyle of the subject. [Periodic abstinence (eg, calendar, ovulation, symptothermal, post-ovulation methods), declaration of abstinence for the duration of a trial, and withdrawal are not acceptable methods of contraception])**, surgical contraceptive methods (vasectomy or bilateral tubal ligation), use of hormonal birth control methods (pills, shots, implants or patches), intrauterine devices (IUDs), or two (2) barrier methods (each partner must use one barrier method) with spermicide – males must use a condom with spermicide; females must choose either a Diaphragm with spermicide, OR Cervical cap with spermicide, OR Contraceptive sponge with spermicide.

- *Note: Additional medications given during treatment with evolocumab may alter the contraceptive requirements. These additional medications may require an increase in the number of contraceptive methods and/or length of time that contraception is to be utilized after the last dose of protocol-required therapies. The investigator is to discuss these contraceptive changes with the study subject.*

[Section: 7, Study Procedures](#)

Add:

In addition to the protocol-specified study procedures and assessments described below, investigators should continue to routinely monitor subjects according to local disease management guidelines and perform assessments (eg ECG, hemoglobin A1c, eGFR, and hematology), as applicable, in routine care.

[Section: 8.1, Removal of Subjects](#)

Replace:

Reasons for removal from protocol-required investigational product might include:

With:

Reasons for removal from protocol-required investigational product include, **but are not limited to:**

Section: Appendix B, Sample Serious Adverse Event Report Form

Replace:

 Evolocumab (AMG 146) 20140128		Clinical Trial Serious Adverse Event Report Phase 1-4 Notify Amgen Within 24 Hours of knowledge of the event				 New  Follow-up				
US: [contact]										
1. SITE INFORMATION										
Site Number		Investigator			Country					
Reporter		Phone Number () ()		Fax Number () ()						
2. SUBJECT INFORMATION										
Subject ID Number		Initials	Date of Birth Day Month Year		Sex  F  M	Race				
3. SERIOUS ADVERSE EVENT - Information in this section must also be entered on the Serious Adverse Event Summary CRF										
Provide the date the Investigator became aware of this Serious Adverse Event information: Day Month Year										
Serious Adverse Event Diagnosis or Syndrome If diagnosis is unknown, enter Signs / Symptoms When Final Diagnosis is known, enter as Adverse Event List one event per line. If event is fatal, enter the Cause of Death. Entry of "Death" is not acceptable, as this is an outcome.	Date Started Day Month Year		Date Ended Day Month Year		Potential Endpoint? Yes/No	Check only if event occurred before first dose of IP	Line Status Check code (see code below) Evolocumab (AMG146) Prefilled Autoinjector/ Pen (AIPen) Device 3.5 mL Personal Injector/ Automated Mini-Doser (AMID) Device	Is there a reasonable possibility that the event may have been caused by IP? (see section 10)	Outcome of Event 01 Fatal 02 Resolving 03 Not resolved 04 Fatal 05 Other significant medical hazard	Check only if event is related to study procedure e.g. biopsy
	Day Month Year		Day Month Year		Yes/No	Yes/No	Yes/No	Yes/No	Yes/No	Yes/No
Serious Criteria: 01 Fatal 03 Required hospitalization 05 Persistent or significant disability/incapacity 07 Other significant 02 Immediately life-threatening 04 Prolonged hospitalization 06 Congenital anomaly / birth defect 08 Other significant medical hazard										
4. HOSPITALIZATION										
				Date Admitted Day Month Year		Date Discharged Day Month Year				
Was subject hospitalized?  No  Yes, if yes, please complete date(s)										
5. INVESTIGATIONAL PRODUCT (IP)										
Initial Start Date Day Month Year		Prior to, or at time of Event Date of Dose Day Month Year		Dose	Route	Frequency	Action Taken with Product 01 Still being Administered 02 Permanently Discontinued 03 Withheld			
Evolocumab (AMG 146) ✓ Open Label										
Prefilled Autoinjector/Pen (AIPen) Device										
3.5 mL Personal Injector/Automated Mini-Doser (AMID) Device										
6. RELEVANT CONCOMITANT MEDICATIONS (e.g. chemotherapy) Any Relevant Medications? No / Yes, if yes, please complete:										
Medication Name(s)	Start Date Day Month Year	Stop Date Day Month Year	Co-suspect Yes/No	Continuing Yes/No	Dose	Route	Freq.	Treatment Med Yes/No		

With:

 evolocumab (AMG 145) 20140128		Clinical Trial Serious Adverse Event Report (3-IMP) Notify Amgen Within 24 Hours of Knowledge of the event						 New  Follow-up						
US: [contact]														
1. SITE INFORMATION														
Site Number		Investigator				Country								
Reporter			Phone Number () ()			Fax Number () ()								
2. SUBJECT INFORMATION														
Subject ID Number		Date of Birth Day Month Year			Sex  F  M	Race								
3. SERIOUS ADVERSE EVENT - Information in this section must also be entered on the Serious Adverse Event Summary CRF														
Provide the date the Investigator became aware of this Serious Adverse Event information: Day Month Year														
Serious Adverse Event Diagnosis or Syndrome If diagnosis is unknown, enter Signs / Symptoms When Final Diagnosis is known, enter as Adverse Event List one event per line. If event is fatal, enter the Cause of Death. Entry of "Death" is not acceptable, as this is an outcome.		Date Started Day Month Year		Date Ended Day Month Year		Potential Endpoint	Check only if event occurred before first dose of IP	Date Serious Adverse Event Occurred (see codes below)	Relationship Is there a reasonable probability that the event may have been caused by: If yes see section 10: evolocumab (AMG 145) Pre-filled autoinjector (open (AI/open)) 3.5 mL personal injector autoinjector mini-doser (AMD)	Outcome of Event 01 Resolving 02 Not resolved 03 Fatal	Check only if event is related to study procedure as depicted			
Serious Criteria: 01 Fatal 02 Immediately life-threatening		03 Required hospitalization 04 Prolonged hospitalization		05 Persistent or significant disability / incapacity 06 Congenital anomaly / birth defect		07 Other significant medical hazard								
4. HOSPITALIZATION														
						Date Admitted Day Month Year		Date Discharged Day Month Year						
Was subject hospitalized?  No  Yes, if yes, please complete date(s):														
5. INVESTIGATIONAL PRODUCT (IP)														
		Initial Start Date Day Month Year			Prior to, or at time of Event Date of Dose Day Month Year			Dose	Route	Frequency	Action Taken with Product 01 Still being Administered 02 Permanently discontinued 03 Withdrawn			
evolocumab (AMG 145) B Open Label														
Pre-filled autoinjector/open (AI/open) B Open Label														
3.5 mL personal injector/autoinjector mini-doser (AMD) B Open Label														
6. CONCOMITANT MEDICATIONS (eg, chemotherapy)														
Any Concomitant Medications? No Yes, if yes, please complete:														
Medication Name(s)		Start Date Day Month Year		Stop Date Day Month Year		Co-escaped No Yes		Continuing No Yes		Dose	Route	Freq.	Treatment Med No Yes

CHD	Coronary heart disease, includes history of myocardial infarction, unstable angina, stable angina, coronary artery procedures (angioplasty or bypass surgery), or evidence of clinically significant myocardial ischemia
CTCAE	NCI Common Terminology Criteria for AEs
CV	Cardiovascular
DBP	Diastolic blood pressure
eCRF	Electronic case report form
EOI	Event of Interest
EOIP	End of Investigational Product
EOS	End of Study (for individual subject)
FAS	Full analysis set
FRS	Framingham Risk Score
HDL-C	High density lipoprotein cholesterol
IAS	Interim analysis set
IP	Investigational product
IPD	Important protocol deviation
LDL-C	Low-density lipoprotein cholesterol
MedDRA	Medical dictionary for regulatory activities
NCEP ATP III TLC	National Cholesterol Education Program Adult Treatment Panel III Therapeutic Lifestyle Changes
NHLBI	National Heart, Lung, and Blood Institute
OLE	Open label extension
QM	Monthly (Every 4 weeks)
SAE	Serious adverse event
SAP	Statistical analysis plan
SBP	Systolic blood pressure

Abbreviation or Term	Definition/Explanation
SC	Subcutaneous
Study day 1	defined as the first day that protocol-specified investigational product is administered to the subject
TEAE	Treatment emergent adverse event
TIA	Transient ischemic attack
ULN	Upper limit of normal
UC	Ultracentrifugation
VLDL-C	Very low-density lipoprotein cholesterol

1. Introduction

The purpose of this Statistical Analysis Plan (SAP) is to provide details of the statistical analyses that have been outlined within the protocol for Evolocumab Study 20140128 dated 22 December 2014 (Amendment 1). The scope of this plan includes the interim analysis and the final analysis that are planned and will be executed by the Biostatistics department unless otherwise specified.

2. Objectives

2.1 Primary

To characterize the safety and tolerability of long-term administration of evolocumab in subjects with known coronary artery disease and hypercholesterolemia.

2.2 Secondary

To characterize the efficacy of long-term administration of evolocumab as assessed by LDL-C in subjects with known coronary artery disease and hypercholesterolemia.

2.3 Exploratory

To evaluate cardiovascular event rates in subjects treated with evolocumab.

3. Study Overview

3.1 Study Design

This is a multicenter, open-label extension study to assess the long-term safety and efficacy of evolocumab. The study endpoints are defined in [Section 4.1](#). Approximately 230 sites in the US, Canada, Latin America, Asia, Australia, South Africa, and Europe will participate in the study. The number of sites may vary depending on the number of subjects from the parent study (20120153). Subjects that successfully complete Week 80 in the parent study (20120153) without discontinuing evolocumab will be eligible to enroll in this study. Subjects will visit the site on Day 1 and week 4. Thereafter, subjects will visit the site quarterly for the first year and two additional times during year 2. All subjects will receive open-label evolocumab for approximately 2 years (or until the investigator's recommendation of discontinuation, Amgen's recommendation of discontinuation, the subject's decision to discontinue for any reason or until an administrative decision is made to end the study).

3.2 Sample Size

The number of subjects entering this study will depend on the number of subjects completing the study 20120153 and their willingness to enroll. Past enrollment rates for other AMG 145 OLE studies were approximately 90%. Assuming 75% of

study 20110153 subjects are completers and eligible to enroll in this study, the sample size will be approximately $950 \times 0.75 \times 0.9 = 642$ subjects.

4. Study Endpoints and Covariates

4.1 Study Endpoints

4.1.1 Primary Endpoint

Subject incidence of adverse events

4.1.2 Secondary Endpoint

LDL-C at Week 52

4.1.3 Safety Endpoints

Changes from baseline in safety laboratory values (including clinical chemistry) and vital signs at each scheduled visit

4.1.4 Exploratory Endpoints

- Subject incidence of adjudicated events
 - death by any cause
 - cardiovascular death
 - myocardial infarction
 - hospitalization for unstable angina
 - coronary revascularization
 - stroke
 - transient ischemic attack (TIA)
 - hospitalization for heart failure
- Subject incidence of non-coronary revascularization
- Change and percent change from baseline at each scheduled visit in each of the following parameters:
 - LDL-C
 - Total cholesterol
 - Non-HDL-C
 - Total cholesterol/HDL-C ratio
 - VLDL-C
 - HDL-C
 - Triglycerides

5. Hypothesis

The primary clinical hypothesis is that long-term exposure of evolocumab will be safe and well tolerated in subjects with known coronary artery disease and

hypercholesterolemia. There will be no formal statistical testing and all statistics will be descriptive in nature.

6. Definitions

6.1 Study Time Points

Enrollment Date

The enrollment date is the day a subject signed the informed consent form for this study.

Study Day 1 (First IP Dose Date)

Study Day 1 is defined as the first day of Investigational Product (IP) administration in this study.

Study Day

For each subject, and for a given date of interest, study day is defined as the number of days since Study Day 1:

$$\text{Study day} = (\text{date of interest} - \text{Study Day 1 date}) + 1$$

If the date of interest is prior to the Study Day 1:

Study day = (date of interest – Study Day 1 date), so that the day prior to Study Day 1 is study day -1.

Last IP Dose Date

For each subject, the Last IP Dose Date is defined as the last day of IP administration in this study:

- If the last dose was administered in-clinic, then Last IP Dose Date is the last start date captured on the IP Administration QM (In-Clinic) eCRF page.
- If the last dose was administered at home, then Last IP Dose Date is defined as the final dose date reported by the subject on the Non-Clinic Final Investigational Product Dose Date eCRF page.

End of Investigational Product (EOIP) Date

The End of Investigational Product Date is the date decision was made to end IP as recorded on the End of IP Administration eCRF page.

End of Study (EOS) Date

For each subject, the End of Study Date is the date recorded on the End of Study eCRF.

Study End Date

The study end date is the last EOS date of all enrolled subjects.

6.2 Demographics and Baseline Related Definitions

Age

Age at baseline is the subject's age at the parent study baseline. Age at enrollment is the subject's age in years as recorded on the enrollment eCRF of this study.

Baseline Values

Baseline values for fasting lipids (total cholesterol, HDL-C, LDL-C, triglycerides, VLDL-C and non-HDL-C) and all other variables are defined as the parent study baseline values.

Change (nominal/absolute change) from Baseline

The arithmetic difference between a post-baseline value and baseline for a given time point:

Change (nominal/absolute change) from baseline = (post-baseline value – baseline value)

Percent Change from Baseline

The percent change from baseline for a given variable at a given time point is defined as:

$100 \times [(value\ at\ given\ time\ point - baseline\ value) / baseline\ value]$

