7.2 General Study Procedures

7.2.1 Enrollment (Week 80 Parent/Day 1 OLE + 14 days)

Day 1 for OLE study and the week 80 visit for the parent study should occur on the same day. All efforts should be made to minimize any time gaps between the parent study EOS and Day 1 in the OLE study. The following procedures will be performed:

- Obtain consent
- Medical History
- Vital signs: sitting blood pressure (BP), heart rate (HR)

- AEs/SAEs/CV Events
- Concomitant medications
- Body weight and waist circumference
- Physical exam
- Blood draw for serum pregnancy (females of childbearing potential only) and FSH (for applicable subjects)
- Blood draw for fasting lipids (≥ 9 hour fasting sample) and chemistry
- Dispense and reconcile IP
- Observe IP Administration evolocumab (AMG 145) QM unless subject elects not to self-inject (must be after completion of vital signs, and blood draw procedures).

Enrollment - subjects will have the risks and benefits of participating in this study explained to them. Subjects that meet inclusion/exclusion criteria will need to sign a new OLE informed consent form, if they already have not done so, before enrolling. Subjects will administered their first injection at the site (must be after completion of vital signs and blood draw procedures). Self-administration, defined as SC administration of IP by the subject or designee, will occur between visits to the investigator site (eg, at home). The patient (or designee) must have demonstrated competency at administration of SC injections before self-administration is permitted: the first two self-administered doses must be administered in a clinic by the patient or designee under the supervision of a healthcare provider. Day 1 is defined as the first day that protocol-specified investigational product is administered.

The following visits are for Year 1 only:

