10.4 Planned Methods of Analysis

10.4.1 General Approach/Considerations

Statistical analyses in this open-label extension study will be descriptive in nature. No statistical inference is planned.

Subject disposition, demographics and baseline characteristics will be summarized.

Summary statistics for continuous variables will include the number of subjects, mean, median, standard deviation or standard error, minimum, and maximum. For categorical variables, the frequency and percentage will be given.

One year interim and final analyses will be based on data collected from this study. Descriptions of any integrated analyses with the parent study are out of scope for this study.

For all endpoints, results will be summarized by the treatment group to which subjects are randomized in Study 20120153, unless otherwise specified.

Unless specified otherwise, the baseline value is defined as the subject's baseline value from the parent study.

There will be no imputation for missing data.

Death, myocardial infarction, hospitalization for unstable angina, coronary revascularization, stroke, TIA, and hospitalization for heart failure will be adjudicated by an independent Clinical Events Committee (CEC) to facilitate aggregated analyses across the program.

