10.4.2.4 Safety Endpoint Analyses

Safety Laboratory Parameters

Laboratory parameters will be summarized using descriptive statistics at each scheduled visit. Laboratory shift tables for certain analytes will be provided using the CTCAE v.4 toxicity criteria. The results will be based on the maximum (ie, worst) shift from baseline to the end of study.

Vital Signs

Vital signs will be summarized using descriptive statistics at each scheduled visit.

Concomitant Medications

Concomitant medications of interest will be summarized.

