10.6.3 Laboratory Test Results

Descriptive statistics will be provided for actual values and changes from baseline in select laboratory parameters at each protocol-specified scheduled visit. Laboratory analytes are provided in the protocol Table 1. Lab shift tables using the CTCAE v4.03 grading will be used for the select analytes of interest, when applicable.

In addition, CK and liver function test (LFT) abnormalities will be assessed by the incidence overall and by visits of the following categories:

- CK > 5 x ULN
- CK > 10 x ULN
- ALT or AST > 3 x ULN
- ALT or AST > 5 x ULN
- Total bilirubin \geq 2 x ULN
- (ALT or AST > 3 x ULN) and Total bilirubin > 2 x ULN and ALP < 2 x ULN

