Appendix A. Analytical Study Week Assignments

Selected endpoints will be summarized by scheduled study visits in descriptive analyses. Since the actual visits may not exactly coincide with their scheduled visit day, the actual visit day is mapped to the study visit generally by non-overlapping consecutive intervals covering the entire time continuum, with scheduled visit time being the center of each interval. The mapping intervals for all distinct schedules are summarized in the following tables.

Handling multiple records assigned to an analytical study week:

If there is more than one record in a study week interval, the analytical record for that specific study week will be defined as the record closest to the scheduled study day of that specific study week ($7 \times \text{study week} + 1$). If two records are equidistant from the scheduled day, then the earlier record will be chosen. If there are multiple records on the same day, the last record will be used.

Scheduled Visit Week	Target Study Day	Vital Signs, Lipids, Chemistry	Physical Measurements
Week 0	1	≤ 1	≤ 1
Week 4	29	(1, 56]	NA
Week 12	85	(56, 126]	NA
Week 24	169	(126, 210]	NA
Week 36	253	(210, 294]	NA
Week 48	337	(294, 350]	NA
Week 52	365	(350, 448]	(1, 546]
Week 76	533	(448, 630]	NA
Week 104	729	> 630	> 546

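### For former-placebo subjects, the laboratory worst-shift tables count persistent grade worsening that arose before the first evolocumab dose and cannot separate it from worsening that began after that dose

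*SAP*

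**What the plan says.** **Baseline.** SAP 6.2 says that values for fasting lipids "and all other variables are defined as the parent study baseline values". Protocol 10.4.1 agrees: "Unless specified otherwise, the baseline value is defined as the subject's baseline value from the parent study". Neither document specifies anything else for laboratory data.

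**Shift tables.** Protocol 10.4.2.4 says of the laboratory shift tables: "The results will be based on the maximum (ie, worst) shift from baseline to the end of study". SAP 10.6.3 plans them as follows: "Lab shift tables using the CTCAE v4.03 grading will be used for the select analytes of interest, when applicable". It neither repeats nor replaces the worst-shift rule.

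**Other laboratory displays.** SAP 10.6.3 also states: "Descriptive statistics will be provided for actual values and changes from baseline in select laboratory parameters at each protocol-specified scheduled visit". CK and liver-test "abnormalities will be assessed by the incidence overall and by visits of the following categories", all defined by multiples of the upper limit of normal.

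**Timing.** Protocol 7.2.1 places extension Day 1 on the same day as the parent week 80 visit, and its heading allows 14 further days. The first extension dose "must be after completion of vital signs, and blood draw procedures". In SAP Appendix A "the actual visit day is mapped to the study visit generally by non-overlapping consecutive intervals", and study day 1 or earlier becomes Week 0.

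**Adverse events.** SAP 6.3 counts an event as treatment emergent only from the first extension dose.

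**The concern.** A worst-shift table in an extension report is naturally read as laboratory change on evolocumab. In the former-evolocumab column that reading is fair, because the parent baseline precedes all exposure. In the former-placebo column the same baseline is followed by about 80 weeks without evolocumab before the extension begins. A shift therefore means something different in each column, and nothing in the table shows it.

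The display serves the primary objective, long-term safety and tolerability. Worsening that belongs to the placebo period may be taken for worsening on drug. The adverse event tables in the same report start from the first extension dose, so the two sets of safety tables would have different starting points for the same subjects. By-visit threshold categories exist only for CK, ALT, AST and total bilirubin, alone or in combination. For any other analyte given a shift table, that table is the only planned categorical laboratory display.

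**Working it through.** **1. Are former-placebo subjects in the study?** Protocol 4 and 7 describe the completed parent product as evolocumab. However, Protocol 2.1 calls the parent trial placebo controlled, SAP 10.1 summarizes results by parent randomized group, and Protocol 7.2.2.5 masks lipids so as not to reveal parent assignment. Former-placebo subjects are therefore included and form their own column.

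**2. How far back is the baseline?** Extension Day 1 is parent week 80: 80 × 7 = 560 days. Parent baseline to extension week 104 is 80 + 104 = 184 weeks, of which 80/184 = 43% precedes the first evolocumab dose. The 80 is approximate, because Day 1 may slip by up to 14 days and the documents do not date the parent baseline value exactly.

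**3. Which values can produce a shift?** SAP 10.1 restricts the analyses to data from this study. Protocol 7.1 schedules chemistry on Day 1 and at weeks 4, 12, 24, 36, 48, 52, 76 and 104. That is 9 draws: 1 before the first extension dose and 8 after it. A worsening on placebo that resolved before Day 1 is not counted. One still present at any of the 8 post-dose draws is.

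**4. What does the table show?** Hypothetical grades for one analyte in former-placebo subjects:

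| Subject | Parent baseline | Day 1, pre-dose | Worst post-dose | Planned shift | Shift from Day 1 | Already worse on Day 1 |
|---|---|---|---|---|---|---|
| A | 0 | 1 | 1 | 0 to 1 | none | yes |
| B | 0 | 0 | 1 | 0 to 1 | 0 to 1 | no |
| C | 0 | 1 | 2 | 0 to 2 | 1 to 2 | yes |
| D | 1 | 0 | 1 | none | 0 to 1 | no |
| E | 0 | 1 | 0 | depends on whether Week 0 counts | none | yes |

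A and B fall in the same cell of the planned table, although A was worse before any evolocumab and B only afterwards. This follows from the stated rules alone. E depends on something the plan does not state.

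**5. Can other planned displays separate A from B?** By-visit summaries include Week 0, so the former-placebo group can be compared before and after first exposure. They are group summaries and do not link a subject's Day 1 grade to that subject's worst grade.

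**6. Size.** The only related figure in the documents is the expected enrolment: 950 × 0.75 × 0.9 = 641.25, rounded up to 642, which reproduces. The parent allocation ratio and the frequency of grade worsening are not given, so what follows is assumption. With half the subjects formerly on placebo, 642/2 = 321. If 0%, 1%, 5% or 10% of them had a Day 1 worsening that persisted after dosing, about 0, 3, 16 or 32 subjects would be counted as shifted for that reason. With one third on placebo, 642/3 = 214, and the counts are about 0, 2, 11 and 21.

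**The case against.** The parent baseline is an openly prespecified choice, stated consistently in both documents. It gives both former groups the same reference. The study is descriptive, and no section calls these shifts treatment emergent. This stands: the plan contains no contradiction or wrong number here, and the parent-baseline table should stay.

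The matter is also partly covered. Week 0 is a summarized visit, SAP 10.6.1 tabulates treatment-emergent muscle and hepatic events of interest, Protocol 9.1.2 makes laboratory changes that need treatment adverse events, and SAP 9.4 provides for documenting any sensitivity analyses required. These limit the consequences, but none supplies the subject-level split.

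Several stronger readings are tempting and should not be drawn:

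- A reader might infer that a worsening seen only in the Day 1 pre-dose sample is counted as a shift, or enters the overall CK and liver incidence. The plan neither includes nor excludes Week 0 there, so this is a request for clarification.
- A reader might infer that all 80 parent weeks are searched for the worst value. SAP 10.1 rules that out; the 80 weeks is only the distance to the reference value.
- A reader might take the 43% in step 2 as the share of shifts that predate exposure. It is a share of time. Turning it into a share of shifts would need assumptions on rates, persistence and dropout that the documents do not give.
- A reader might count the analytes that depend on the shift table alone. SAP 10.6.3 does not name the selected analytes, so no count is supported.

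**Conclusion.** The point holds in a narrow form. Under the stated rules, a former-placebo subject whose grade worsened before the first evolocumab dose and stayed worse at a post-dose visit is counted as shifted. The planned table cannot distinguish that subject from one who first worsened on evolocumab.

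This rests on the worst-shift rule in Protocol 10.4.2.4 still governing the SAP tables, and on no baseline exception being set elsewhere. The size is unknown and may be zero; the counts in step 6 illustrate assumed rates and are not estimates. The primary endpoint, LDL-C at week 52 and the treatment-emergent adverse events are untouched. It is an optional improvement to one safety display.

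**What to change.** Keep the parent-baseline shift tables as the common display, and make these changes:

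- **SAP 6.2:** define an extension baseline as the last value on or before the first extension dose.
- **SAP 10.6.3, new tables:** for the placebo-to-evolocumab group, add CTCAE worst-shift tables from the extension baseline, using post-dose values only. These show worsening relative to the pre-dose grade.
- **SAP 10.6.3, flag:** in the parent-baseline table, mark the subjects whose Day 1 pre-dose grade was already worse than at parent baseline. The extension-baseline table alone does not give this split: it counts subject C, who was already worse on Day 1, and subject D, who never exceeded the parent-baseline grade.
- **Clarification:** state whether the Day 1 (Week 0) sample counts in the parent-baseline worst shift and in the overall CK and liver categories, and keep Protocol 10.4.2.4 consistent with the answer.

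Protocol 10.4.1 allows a different baseline where one is specified, and the Day 1 chemistry sample is already scheduled. The cost is one derived baseline variable, one flag and one extra set of tables. Without a control group, the added display separates worsening before first exposure from worsening after it; it does not isolate a drug effect.
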